## 1.2.2 Data Safety Monitoring Board

An independent Data Safety Monitoring Board (DSMB) will be monitoring data from the study on a monthly basis throughout Part 1 to ensure the safety of the patients in the trial.

An independent statistical group, Statistics Collaborative, Inc., will prepare unblinded analyses for the DSMB and will not have a role in the statistical analysis plan (SAP) or day-to-day support of the study.

#### 1.2.3 Discontinuation of Treatment

Discontinuation refers to a patient stopping administration of study drug. Reasons for study drug discontinuation may include the following:

- Occurrence of an adverse event or change in medical status that leads the investigator to be concerned about the patient's welfare
- Protocol violations
- Administrative reasons (e.g., inability to continue)
- Sponsor termination of the study
- Voluntary withdrawal
- Pregnancy during the study
- Investigator unblinding
- Other

Patients who are discontinued from study drug should still complete all study visits and undergo all scheduled study assessments, if possible.

#### 1.2.4 Patient Termination

Termination refers to a patient stopping study drug and all study assessments and visits. Reasons for study termination include the following:

- Administrative reasons (e.g., inability to continue, lost to follow-up)
- Death
- Withdrawal of consent

Patients who terminate the study for any reason may not re-initiate study drug or study assessments at any time.

#### 1.2.5 Randomization and Unblinding

The first cohort enrolled in Part 1 will be randomized 3:1 to RTA 408 2.5 mg or placebo. After the Week 2 visit, each patient in the first cohort will dose escalate to 5 mg (or remain on placebo) and remain on 5 mg through the remaining 10 weeks of treatment. Beginning with the second cohort enrolled in Part 1, patients will be randomized 3:1 to a specific dose of RTA 408 or placebo as recommended by the DSMB. Patients will remain at their randomized dose through the entire 12 weeks of treatment.

To maintain the study blind, all study drug kits will be packaged with blinded labels. Investigators will distribute the blinded study drug kits by kit number to patients as assigned by the IWRS. All patients, investigators, site personnel, and laboratories with direct involvement in the conduct of the study or their designees will be blinded to treatment assignments and

appropriate measures will be taken to ensure the blind is maintained to reduce potential bias. Some Sponsor personnel may have access to treatment assignments during dose escalation (Part 1).

## 1.3 Sample Size and Power

The sample size for Part 1 (i.e., 8 per cohort for 64 total patients in Part 1) is based on a dose-escalation scheme to evaluate initial safety and PD activity of RTA 408 in this patient population. The small number of patients at each dose in Part 1 is not expected to fully characterize safety, efficacy, or PD, but rather inform the DSMB and Sponsor of the appropriate doses to select for Part 2.

#### 2. PLANNED ANALYSIS OF PART 1

This study consists of two distinct parts: a placebo-controlled, dose-ranging part (Part 1) followed by a second placebo-controlled part (Part 2) utilizing one dose selected from Part 1. Analyses planned for Study Part 2 will be described in a separate document.

#### 2.1 Interim Analysis

A DSMB will be reviewing data on an ongoing basis from the study to ensure patient safety. The DSMB will not recommend stopping the study for efficacy. The DSMB charter describes the interim reviews of safety. No other formal interim analyses are planned for this study.

## 2.2 Timing of Analysis

The primary analysis of Part 1 will be performed after all patients enrolled in Part 1 have completed Part 1 and the Part 1 records are locked in the EDC system. Other analyses of Part 1 data may be performed prior to database lock in order to plan for Part 2 of this study.

## 2.3 Endpoint Measures

Unless otherwise specified, efficacy measures are obtained for all patients.

## 2.3.1 Efficacy Endpoints

The primary efficacy endpoint is change in peak work. Peak work will be derived by dividing the maximum work load (watts) at each visit by the patient's baseline weight (kg). Peak work will be rounded to the 0.0001 digit.

The secondary efficacy endpoint is the change in 6-minute walk test (6MWT) distance.

Exploratory endpoints for this trial include:

- To evaluate the change in peak oxygen utilization during maximal exercise testing
- To evaluate the change in peak blood lactate and pyruvate, peak heart rate, and rating of perceived exertion during submaximal exercise testing
- To evaluate the change in Fatigue Severity Scale score
- To evaluate the change in SF-36® Health Survey Update (SF-36) score
- Parameters assessed from blood lactate and serum pyruvate during submaximal exercise testing

## 2.3.2 Safety Endpoints

Safety parameters include results of echocardiogram, ECG, vital sign measurements, weight, BMI, physical examination, AEs, SAEs, concomitant medications, and laboratory tests (clinical chemistry, hematology, urinalysis, microscopy, and pregnancy tests [as indicated]).

# 2.4 Changes from Protocol-Specified Analysis

There are no planned changes to analyses from what is described in the protocol.

#### 3. GENERAL CONSIDERATIONS FOR DATA ANALYSIS

#### 3.1 Analysis Considerations

All individual data will be listed as recorded in the database. All statistical summaries and analyses will be performed using SAS® software (SAS Institute, Cary, North Carolina, USA).

Only patients in the appropriate analysis set will be included in summary statistics. For endpoints discussed in this SAP, all available data for each patient will be included in summaries.

Patients randomized to RTA 408 in cohort 1 will escalate from 2.5 mg to 5 mg at Week 2. These patients will be categorized as the 5-mg treatment group for data presentations. Patients enrolled in all other cohorts will remain on their randomized dose for all 12 weeks of treatment, and will be categorized according to their randomized treatment for data presentations. Patients randomized to placebo within each cohort will be pooled for data presentations into a single placebo treatment group.

All raw patient data will be converted to SDTM for submission to FDA, however, only the analysis data will be presented in individual-patient data listings.

Continuous data will be summarized by treatment using descriptive statistics (number, mean, standard deviation [SD], minimum, median, quartiles (Q1, Q3), and maximum). Categorical data will be summarized by treatment using frequency tables (number and percentage).

## 3.2 Analysis Sets

For Part 1 of the study, the following analysis sets will be defined.

#### 3.2.1 Full Analysis Set

The full analysis set (FAS) includes all enrolled patients in Part 1, whether or not they received study drug. The FAS will be used to assess patient disposition and efficacy endpoints. Patients will be summarized according to the treatment to which they were randomized.

## 3.2.2 Safety Analysis Set

The safety analysis set includes all patients who received at least 1 dose of study drug. The safety analysis set will be used to assess safety endpoints. Patients who receive at least 1 dose of RTA 408 will be classified in the RTA 408 group at the highest dose level received.

#### 3.2.3 Pharmacokinetic

The Pharmacokinetic analysis set will be a stand-alone analysis.

#### 3.3 Strata and Covariates

Randomization in Part 1 of this study is not stratified. Since sample size per dose level will be small, no covariates will be considered for the primary analysis of Part 1.

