### 8. SELECTION AND WITHDRAWAL OF PATIENTS

### 8.1. Patient Inclusion Criteria

Patients must:

- 1. Have mitochondrial myopathy as evidenced by the following 2 criteria (must meet both):
  - a. Have a history of exercise intolerance with or without weakness and/or progressive exercise intolerance (in which modest exercise typically provokes heaviness, weakness, aching of active muscles, or tachycardia)
  - b. Have a known primary mitochondrial DNA mutation or a nuclear DNA defect that is associated with reduced activity of at least 1 mitochondrially encoded respiratory chain complex
- 2. Be male or female and  $\geq 18$  years of age and  $\leq 75$  years of age
- 3. Have no changes to their exercise regimen within 30 days prior to Study Day 1 and be willing to remain on the same exercise regimen during the 16-week study period
- 4. Have the ability to complete maximal exercise testing
- 5. Have peak work during maximal exercise testing of  $\leq 1.5$  W/kg
- 6. Have adequate kidney function defined as an estimated glomerular filtration rate (eGFR) ≥60 mL/min/1.73 m^2 using the Modification of Diet in Renal Disease (MDRD)
  4-variable formula
- 7. Be able to swallow capsules
- 8. Be willing and able to cooperate with all aspects of the protocol
- 9. Be willing to practice the medically acceptable methods of birth control (Section 9.7.2)
- 10. Provide written informed consent for study participation, approved by the appropriate Institutional Review Board (IRB) or Ethics Committee (EC)

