#### 9.9.25. Submaximal Exercise Test

Cycle ergometry will be used to conduct submaximal exercise tests at the times indicated in Table 3. Patients will perform the submaximal exercise testing at the subset of sites selected by the Sponsor, and submaximal exercise testing assessments will be required for all patients enrolling at these selected sites. Specific instructions will be provided in a study manual. Submaximal exercise test assessment may include but are not limited to submaximal work, peak serum lactate and pyruvate (optional), peak heart rate, and peak rating of perceived exertion. As part of the submaximal exercise test, additional blood samples to measure serum lactate will be collected at rest and at 10-minute intervals throughout the test. At Sponsor-qualified sites, blood samples to measure serum pyruvate, potassium, and glucose will be collected at rest and at 10-minute intervals throughout the test.

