#### 14.3.2. Primary Efficacy Analysis

Primary analysis of the efficacy data will be based on the mITT population, which will include all patients randomized in Part 2 of the study. Peak work from Part 2 for the pooled patients treated with RTA 408 will be compared with placebo after 12 weeks of treatment by repeated measures analysis of covariance, with treatment group, time, and the interaction between treatment and time as fixed factors and baseline peak work as a covariate. The difference between RTA 408 and placebo in change from baseline of mean peak work will be estimated along with the 95% confidence interval of the difference. The SAP will describe the strategy used to control the Type I error rate when comparing each dose of RTA 408 with placebo\$

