## 1.2 Part 1 Study Design

Part 1 of this study will evaluate the efficacy, safety, PK, and PD of RTA 408 in the treatment of up to approximately 64 patients with mitochondrial myopathy.

The first part of the MOTOR study will be a randomized, placebo-controlled, double-blind, dose-escalation study to evaluate the safety of RTA 408 at 2.5 mg, 5 mg, 10 mg, 20 mg and higher dose levels (not to exceed 160 mg) in up to approximately 8 cohorts of patients with mitochondrial myopathy. A cohort consists of the next eight eligible patients randomized 1:3 to placebo (n=2) or the cohort specific dose of RTA 408 (n=6). Up to 8 cohorts will be enrolled in Part 1 to allow for adequate dose-ranging for selection of RTA 408 dose(s) to be used in Part 2.

Intra-patient dose-escalation will only be utilized in the first cohort to evaluate RTA 408 at the first two dose levels (2.5 mg and 5 mg). Patients enrolling in the first cohort will be randomized to RTA 408 2.5 mg or placebo. After the Week 2 visit, each patient in the first cohort will dose escalate to 5 mg (or remain on placebo) on Day 15 unless a dose-limiting toxicity (DLT) is reported in that patient. After the last patient in the first cohort completes their Week 4 visit (i.e., 2 weeks on 2.5 mg daily [or matching placebo] followed by 2 weeks on 5 mg daily [or matching placebo]), the data safety monitoring board (DSMB) and Sponsor will review all available safety information and make a decision regarding enrollment of the next cohort. Beginning with the second 8-patient cohort, once the eighth patient enrolled completes their Week 2 visit the DSMB will review all available safety information and recommend the dose of RTA 408 for the subsequent cohort. The DSMB dose recommendation for each cohort must not exceed 100% more than the highest dose of RTA 408 evaluated in this study, and the maximum permitted dose of RTA 408 is 160 mg. The dose-level for each new cohort will not exceed the DSMB recommended dose level, and it will be selected by the Sponsor based on review of available safety, efficacy, PK, and PD data. Prior to opening each cohort in Part 1 for enrollment, the Sponsor will evaluate all available data from doses studied in Part 1 to determine if enough information is available to select doses for Part 2 of the study. Once doses are selected for Part 2 by the Sponsor, no additional cohorts will be enrolled in Part 1.

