## 6.1 Primary Efficacy Analysis

Peak work (w/kg) is calculated as the maximum workload (w) at each visit divided by baseline weight (kg) for each patient. Peak work should be rounded to the nearest 0.0001 digit. A mixed-model for repeated measures (MMRM) analysis will be used to analyze the primary efficacy variable. All scheduled peak work values collected through the Week 12 visit will contribute to the primary analysis. The primary efficacy variable, the change from baseline in peak work value, will be calculated for each post first dose time point through Week 12 visit (i.e., Weeks 4 and 12). Missing data for the Phase 2 portion will not be imputed for the primary analysis. The primary inference will be the test of LS mean at each time point. The primary endpoint is the mean change from baseline in peak work at Week 12.

Patients must complete the maximal exercise test for at least 4 minutes to be considered a valid test. Maximal exercise test trials which were 4 minutes or less in duration will not be used in the primary efficacy analysis.

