#### 6.1.2 Statistical Model

The MMRM model will include change from baseline in peak work as the dependent variable, treatment group, protocol scheduled time point (analysis visit), and the interaction between treatment and time as fixed effects, patient as a random effect. Analysis visits 0, 4, and 12 will be used. Within-patient correlations will be modeled using an unstructured covariance structure. Time ordering is a repeated measure within patients. It is assumed that errors for different patients are independent with an unstructured covariance structure. The estimation method for the model will be restricted maximum likelihood (REML). The SAS pseudo-code is as follows:

```
proc Mixed data=efficacy method=reml;
  Class usubjid trt avisit;
  model resp=trt avisit trt*avisit /s;
  repeated avisit / subject=usubjid type=un rcorr;
  lsmeans trt*week / diff cl alpha=0.05;
run;
```

In the event the MMRM model with an unstructured covariance structure does not converge, the following covariance structures will be as substitution in the following order. Each subsequent covariance structure will be used only if all previous covariance structure(s) is (are) used and the model(s) did not converge.

 Toeplitz covariance structure (assuming measurements from samples taken closer together in time are more highly correlated than those from samples taken farther apart).

Version 1 Date: 03Mar2018

- First order of auto-regressive [AR(1)] covariance structure (assuming measurements from samples taken closer together in time are more highly correlated than those from samples taken farther apart).
- Compound symmetry covariance structure (assuming equal correlation for measurements from a patient, regardless of how far apart in time when they were taken).

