#### 6.3 Exploratory Efficacy

Summary statistics and 95% confidence intervals for treatment differences in mean change from baseline, using the same MMRM model used for the primary and secondary endpoints, will be provided for all exploratory endpoints unless otherwise noted. P-values will be provided for descriptive purposes only.

For parameters having repeated measurements within an analysis visit during the maximal and submaximal exercise test, the MMRM code should incorporate the analysis visit and assessment time (during the exercise test) in the analysis:

```
Proc Mixed data=x order=data;
Class patno trt week;
model resp = trt*time*week /s;
Repeated time*week / sub = patno type = un;
```

```
lsmeans trt*time*week / diff cl alpha=0.05;
Run;
```

For blood lactate measurements during the submaximal exercise test, the repeated measures model will incorporate baseline resting blood lactate as a covariate:

```
Proc Mixed data=x order=data;
  Class patno trt week;
  model resp = trt*time*week baseline_resting_lactate /s;
  Repeated time*week / sub = patno type = un;
  lsmeans trt*time*week / diff cl alpha=0.05;
  Run:
```

As with the primary and secondary endpoints, exploratory endpoints will be analyzed using individual doses of RTA 408 versus placebo pooled. A separate model that does not pool the RTA 408 doses will be used to obtain pairwise differences for each dose level versus pooled placebo.

For parameters having repeated measurements within an analysis visit during the maximal and submaximal exercise test, the change from resting (delta) for parameters measured at resting and a certain timepoint during the maximal or submaximal exercise test will be reported as:

Delta = [Parameter at Y min] – [Parameter at resting]

In the maximal exercise test, laboratory measurements may be measured at resting, at the end of the maximal exercise test, 5 min after the end of the maximal exercise test, and 10 min after the end of the maximal exercise test.

In the submaximal exercise test, efficacy and laboratory measurements are recorded at resting, at 10 min, 20 min, and 30 min.

The change from baseline is defined for parameters measured at resting and a certain timepoint during the maximal of submaximal exercise test is defined as:

Change from Baseline in Delta= [Parameter at Y (At Visit X) - Parameter at resting(At Visit X)] - [Parameter at Y min (At Baseline) - Parameter at resting(At Baseline)]

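### Small dose groups do not justify leaving baseline peak work out of the Part 1 primary model (SAP 3.3); adding it is a cheap gain in precision

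*SAP*

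**What the plan says.** SAP 3.3 notes that Part 1 randomisation is unstratified and continues: "Since sample size per dose level will be small, no covariates will be considered for the primary analysis of Part 1". SAP 6.1.2 follows this. The response is change from baseline in peak work, and the fixed effects are treatment, visit and their interaction ("model resp=trt avisit trt*avisit /s").

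Elsewhere the plan does adjust for a baseline value:

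- For submaximal lactate in Part 1, SAP 6.3 states that "the repeated measures model will incorporate baseline resting blood lactate as a covariate". Fewer patients may contribute there, since Protocol 9.9.25 says "Patients will perform the submaximal exercise testing at the subset of sites selected by the Sponsor".
- For Part 2, with 8 patients per group, Protocol 14.3.2 specifies treatment, time, the "interaction between treatment and time as fixed factors and baseline peak work as a covariate".

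SAP 3.3 limits its rule to the Part 1 primary analysis, and the protocol gives no Part 1 model. These passages therefore do not contradict one another.

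**The concern.** The number of patients per dose does not determine whether one baseline slope can be estimated. The slope is shared by all groups, so its precision depends on total Part 1 enrolment. Baseline peak work is also on file for every eligible patient, because Protocol 8.1 makes it an entry criterion ("Have peak work during maximal exercise testing of" at most 1.5 W/kg).

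Analysing change from baseline amounts to fixing the baseline slope at 1. If the true slope is lower, chance baseline imbalance is over-corrected and adds noise to each comparison. Small unstratified groups make such imbalance larger, which favours adjusting.

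What is at stake is the width of the interval for each dose, which rests on six treated patients. There is also a smaller loss. The rationale for SAP Version 2.0 says that Part 1 learning can feed the Part 2 analysis. The planned Part 1 model does not estimate the baseline slope that the protocol's Part 2 model needs.

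**Working it through.** **Inputs from the documents**

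- Six active and two placebo patients per cohort, "in up to approximately 8 cohorts of patients with mitochondrial myopathy" (SAP 1.2), 64 patients in all (SAP 1.3).
- Placebo pooled over cohorts (SAP 3.1): 16 with eight cohorts, 8 with four, 4 with two.
- SD 0.28 W/kg, effect 0.28 W/kg, two-sided 0.05, compound symmetry with rho = 0.20 (Protocol 14.1, for Part 2). Protocol 14.1.1 compares the pooled baseline SD with 0.28, so I use 0.28 as the baseline SD.

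**Assumed, because the documents do not give them:** the baseline-to-Week 12 correlation, rho, and k = Week 12 SD / baseline SD.

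**The plan's own figure.** Part 1 has no power calculation. The Part 2 figure of about 80% reproduces as follows.

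- The SD of the mean of two post-baseline visits is 0.28 × sqrt((1 + 0.20)/2) = 0.2169.
- After the allowed drop-outs, 7 versus 14 remain. SE = 0.2169 × sqrt(1/7 + 1/14) = 0.1004, and power = Phi(0.28/0.1004 − 1.96) = 79.6%.
- For 36 patients with SD 0.35 and 11 versus 22, the same steps give 79.9%.

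These match with 0.20 as the correlation between the two post-baseline visits and baseline unused. The 0.20 is therefore not shown to be the correlation needed here, and I use a range.

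**Degrees of freedom.** These counts take each cohort as a separate dose. Cohort 1 counts once, as 5 mg (SAP 3.1).

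- Eight cohorts: 64 − 9 groups = 55, falling to 54 with one slope. Critical t goes from 2.0040 to 2.0049.
- Four cohorts: 32 − 5 = 27, falling to 26. Critical t goes from 2.0518 to 2.0555.
- Two cohorts: 16 − 3 = 13, falling to 12. Critical t goes from 2.1604 to 2.1788.

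**Standard errors at Week 12, one dose (n = 6) against pooled placebo**, with f = sqrt(1/6 + 1/n_placebo):

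- Unadjusted: 0.28 × f × sqrt(1 + k² − 2·rho·k)
- Adjusted: 0.28 × f × k × sqrt((1 − rho²)(1 + 1/(df − 2))), where df is the unadjusted value. The last factor is the expected cost of estimating the slope.

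Example with eight cohorts, k = 1 and rho = 0.5: f = sqrt(1/6 + 1/16) = 0.4787 and 0.28 × f = 0.1340.

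- Unadjusted SE = 0.1340 × sqrt(1) = 0.1340.
- Adjusted SE = 0.1340 × sqrt(0.75 × (1 + 1/53)) = 0.1172.
- Ratio = 1.144.

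The 0.134 W/kg is also the SD of chance baseline imbalance, about half the 0.28 W/kg planning effect.

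Ratio of unadjusted to adjusted SE (above 1 favours adjusting):

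| Cohorts | k | rho 0.5 | rho 0.7 | rho 0.8 | rho 0.9 |
|---|---|---|---|---|---|
| 8 | 0.9 | 1.213 | 1.143 | 1.116 | 1.101 |
| 8 | 1.0 | 1.144 | 1.075 | 1.044 | 1.016 |
| 8 | 1.1 | 1.096 | 1.032 | 1.007 | 0.991 |
| 4 | 0.9 | 1.200 | 1.132 | 1.105 | 1.090 |
| 4 | 1.0 | 1.132 | 1.064 | 1.034 | 1.006 |
| 4 | 1.1 | 1.085 | 1.022 | 0.997 | 0.981 |
| 2 | 1.0 | 1.106 | 1.039 | 1.009 | 0.982 |
| 2 | 1.1 | 1.059 | 0.998 | 0.973 | 0.958 |

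Simulation (40,000 trials per setting, eight and four cohorts, k = 1.0 and 1.1) agrees to within 0.002. If 0.20 were the baseline-to-Week 12 correlation, the excess with eight cohorts and equal SDs would be 28%.

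**95% CI half-widths (W/kg), eight cohorts, equal SDs, unadjusted versus adjusted:** 0.269 and 0.235 at rho 0.5, 0.208 and 0.194 at 0.7, 0.170 and 0.163 at 0.8.

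**Where adjusting stops helping.**

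- Equal SDs: the CI break-even rho is about 0.96 with eight cohorts, 0.92 with four, 0.88 with three and 0.80 with two.
- k = 1.1: adjusting gives a slightly wider interval for rho of about 0.83 to 0.95 (eight cohorts) or 0.78 to 0.96 (four). The lowest SE ratios are 0.991 (eight), 0.981 (four) and 0.957 (two), so the SE cost is at most about 1%, 2% and 4%.

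**The case against.** The change-score analysis is pre-specified, valid and consistently implemented, so preferring a baseline-adjusted model is a matter of efficiency. That stands.

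The gain depends on two quantities that the documents do not give. At rho 0.8 with equal SDs and eight cohorts it is 0.170 − 0.163 = 0.007 W/kg in half-width. With k = 1.1 it nearly vanishes. The 1.5 W/kg entry cap restricts baseline but not Week 12, so k above 1 is at least plausible. This also stands, and it is why a range is shown.

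Part 1 ends once doses are chosen. With only two cohorts, caution about extra terms is defensible, since the break-even correlation is then about 0.80.

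The comparisons with other analyses are imperfect:

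- Part 2 is stratified by baseline peak work, and its primary contrast pools the doses (16 versus 8).
- The lactate endpoint is exploratory. Its covariate is resting lactate, while its response is a change in the rise from rest. SAP 3.4 suggests a specific interest in resting lactate.

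These points weaken the analogies. They do not rescue the stated reason, because a common slope is not estimated dose by dose.

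Finally, no decision is shown to turn on this. The model is run after Part 1 lock for the study report (SAP 1), earlier planning analyses are allowed (SAP 2.2), and Part 1 is not expected to characterise efficacy fully (SAP 1.3). That limits the weight of the point.

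**Conclusion.** The concern holds as a recommended improvement in precision. It does not show a bias or a contradiction. The reason in SAP 3.3 is unsound: at planned enrolment the adjustment costs one or two of about 55 degrees of freedom. With equal SDs and eight cohorts, the unadjusted standard error is 2% to 14% larger for correlations from 0.9 down to 0.5. The possible loss from adjusting is about 1% with eight cohorts, rising to about 4% if only two enrol.

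The figures assume an SD of 0.28 W/kg carried over from Part 2 planning, complete data, a separate dose for each cohort, and an unstructured covariance over post-baseline visits, so that the Week 12 contrast equals a Week 12 ANCOVA. The statement that there is no bias rests on randomisation. Placebo is pooled over cohorts enrolled in sequence, so it also assumes that those cohorts are comparable.

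**What to change.** Before Part 1 database lock, amend SAP 3.3 and 6.1.2 to include baseline peak work and its interaction with visit:

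`model resp = base trt avisit trt*avisit base*avisit`

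Keep the unadjusted change from baseline as a sensitivity summary. Make the matching change for baseline 6-minute walk distance in SAP 6.2. The gain there may be smaller, because SAP 3.7.2 averages two tests for that baseline, which lowers the baseline SD relative to Week 12.

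As a separate repair to the same model text, reconcile the visit lists. SAP 6.1.2 and 6.2 include analysis visit 0, whereas SAP 6.1 says the response "will be calculated for each post first dose time point through Week 12 visit (i.e., Weeks 4 and 12". Change at visit 0 is zero for every patient, so listing it does not adjust for baseline, and the zeros prevent a proper unstructured fit. Post-baseline visits should supply the response, and visit 0 should supply the covariate.

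The cost is SAP wording and two model terms, with no new data collection. It uses one or two of about 55 degrees of freedom, or of about 27 with four cohorts.
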